4 STUDY OBJECTIVES

4.1 *Efficacy*

4.1.1 Primary Objective

The primary objective of this study is to evaluate the effect of CardiolRx™ on prevention of cardiovascular and COVID-19 complications in patients hospitalized for COVID-19.

4.1.2 Primary Efficacy Outcome

The primary composite endpoint in this study is to experience one of the following events during the first 28 days post randomization:

- All-cause mortality
- Requirement for ICU admission and/or ventilatory support due to COVID-19
- CV complications*:
 - HF or
 - AMI or
 - myocarditis
 - new sustained or symptomatic arrhythmia or
 - stroke

*see Appendix 17.8 for definitions

4.1.3 Secondary Efficacy Objectives

Secondary objectives include the improvement in other clinical parameters during 28 days post randomization.

4.1.4 Secondary Efficacy Parameters

The secondary efficacy parameters include the following:

- ...Win Ratio of Ordinal Outcome Scale endpoint:
 - 1) not hospitalized and no limitations of activities;
 - 2) not hospitalized, with limitation of activities, home oxygen requirement, or both;
 - 3) hospitalized, not requiring supplemental oxygen and no longer requiring ongoing medical care
 - 4) hospitalized, not requiring supplemental oxygen but requiring ongoing medical care
 - 5) hospitalized, requiring any supplemental oxygen;
 - 6) hospitalized, requiring noninvasive ventilation or use of high-flow oxygen devices;
 - 7) hospitalized, receiving invasive mechanical ventilation or extracorporeal membrane oxygenation (ECMO);
 - 8) MI or stroke diagnosed since randomization
 - 9) death.
- Change in hs-troponin from baseline to peak elevation during the 28-day treatment period
- Change in TNF-alpha from baseline to peak elevation during the 28-day treatment period

4.1.5 Other Efficacy Parameters

Other efficacy parameters include the following:

- Percentage of patients developing any one of the primary endpoint components within 60 days post randomization
- CV mortality at 28 days post randomization
- Percentage of patients requiring dialysis within 28 days post randomization
- Win ratio of the Ordinal Outcome Scale endpoint within 60 days of randomization
- PICQ at Day 28 and at Day 60
- Development of severe lymphopenia, defined as < 1000 cells/ microliter within 28 days post randomization
- Change in (elevation of) hs-troponin, NT-proBNP, D-dimer and in inflammatory markers (hs-CRP, ferritin, TNF-alpha, IL-1 beta, IL-6, IL-10) from baseline to Day 7 (AUC)
- Change from baseline to peak elevation of NT-proBNP, D-dimer and in inflammatory markers (hs-CRP, ferritin, IL-1 beta, IL-6, IL-10) during the 28-day treatment period
- Change from baseline to peak elevation of LDH during the 28-day treatment period
- Difference in CMR parameters: LVEF, LVEDV, LVESV, LAESV, ECV, GLS, LV mass, LGE extent and edema between the two treatment groups after 4 weeks of study treatment (in a subset of patients at selected sites).

4.2 Safety

4.2.1 Safety Objective

The primary safety objective is to demonstrate that administration of CardiolRx™ in the proposed doses in this patient population is safe.

4.2.2 Primary Safety Endpoints

The primary safety endpoint is the number of SAEs and AEs during the 60-day study period.

4.2.3 Secondary Safety Endpoints

The secondary safety endpoints include changes in C-SSRS, blood chemistry and hematology parameters (including lymphocyte count), ALT, AST, bilirubin, eGFR, creatinine, INR and QTc interval from ECG recordings 5 hours post morning dose (time window 3.5 – 6 hours) during 28 days of study drug administration.

4.3 Study Drug Levels

CBD levels will be measured at baseline, at Days 3, 5, 7, and 28.

5 STUDY POPULATION

5.1 *Enrolment and Study Centers*

422 patients will be randomized (211 to CardiolRx™ and 211 to placebo) in this multi-centre trial.

5.2 *Inclusion Criteria*

The following inclusion criteria must be met to enroll a patient into this study:

1. Males and females 18 years of age or older
2. Hospitalized for COVID-19 with the most recent test positive*; not receiving or likely to receive invasive mechanical ventilation within the next 24 hours
3. Prior history of at least one of:
 - i) CVD [cardiovascular (CV), cerebrovascular or peripheral vascular diagnoses],
 - ii) Age > 64,
 - iii) Diabetes (DM),
 - iv) Hypertension (HTN),
 - v) Abnormal serum lipids,
 - vi) Obesity (BMI \geq 30 or waist circumference >102 cm [40"] for men and >88 cm [35"] for women),
 - vii) Current smoker

* Must be PCR test.

5.3 *Exclusion Criteria*

None of the following criteria can be present if a patient is to be enrolled in this study:

1. Patients who have received vasopressors, extracorporeal membrane oxygenation and mechanical ventilation within last 30 days
2. Background of cardiac transplant surgery
3. Implanted defibrillator (ICD) in the last month
4. Implanted left-ventricular assist device (LVAD)
5. Acute coronary syndrome (ACS) within 30 days
6. Percutaneous coronary intervention (PCI) within 30 days
7. Receiving immuno-suppressive therapy other than dexamethasone
8. History of QT interval prolongation
9. Treated with strong inducers CYP3A4 or CYP2C19, as listed in Appendix 17.7
10. QTc interval > 500 msec (please refer to section 9.2.3 for BBB correction)
11. Chronic renal failure, as defined as eGFR < 30 ml/min

- 12. Elevated alanine aminotransferase (ALT) or aspartate aminotransferase (AST) > 5 times the upper limit of normal (ULN) **or** Alt or AST >3x ULN plus bilirubin >2x ULN
- 13. Bacterial sepsis, defined as documented bacteremia at the time of presentation or other active bacterial infection
- 14. Current participation in any research study involving investigational drugs or devices with the exception of dexamethasone, remdesivir, baricitinib plus remdesivir, convalescent plasma or monoclonal antibodies against the SARS-CoV-2 virus or any other therapy approved under emergency use in the region for treatment of COVID-19
- 15. Inability or unwillingness to give informed consent
- 16. Ongoing drug, alcohol or cannabis abuse (in the opinion of the investigator)
- 17. Women who are pregnant or breastfeeding
- 18. Any factor, which would make it unlikely that the patient can comply with the study procedures
- 19. Hemoglobin < 8.5 gm/dL
- 20. Leukocyte count < 3000/ mm³
- 21. Platelets < 100,000 / mm³
- 22. Current diagnosis of cancer, with the exception of non-melanoma skin cancer
- 23. Showing suicidal tendency as per the C-SSRS, administered at screening
- 24. Any cannabinoid intake in the past month
- 25. Body weight > 170 kg

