1 STUDY SYNOPSIS

Protocol Title	Study to evaluate the Efficacy and Safety of CardiolRx™ in Patients with COVID-19 and Cardiovascular Disease or Risk Factors A double-blind, placebo-controlled Phase II/III Study (LANCER)
Diagnosis	Non-critical patients, hospitalized for COVID-19 with a prior history of cardiovascular disease (CVD) and/or at least one risk factor for CVD
Inclusion Criteria	
 1. Males and females 18 years of age or older 2. Hospitalized for COVID-19 with most recent test positive*; not receiving, or likely to receive invasive mechanical ventilation within the next 24 hours 3. Prior history of at least one of: 
 i) CVD [cardiovascular (CV), cerebrovascular or peripheral vascular diagnoses], ii) Age > 64, iii) Diabetes (DM), iv) Hypertension (HTN), v) Abnormal serum lipids, vi) Obesity (BMI\geq30 or waist circumference >102 cm [40"] for men and >88 cm [35"] for women), vii) Current smoker
	* Must be polymerase chain reaction (PCR) test.
Exclusion Criteria	
 1. Patients who have received vasopressors, extracorporeal membrane oxygenation and mechanical ventilation within last 30 days 2. Background of cardiac transplant surgery 3. Implanted defibrillator (ICD) in the last month 4. Implanted left-ventricular assist device (LVAD) 5. Acute coronary syndrome (ACS) within 30 days 6. Percutaneous coronary intervention (PCI) within 30 days 7. Receiving any immuno-suppressive agent other than dexamethasone 8. History of QTc interval prolongation 9. QTc interval > 500 msec (see section 9.2.3 for bundle branch block [BBB] correction)

10. Treated with strong inducers of CYP3A4 or CYP2C19, as listed in Appendix 17.7
11. Chronic renal failure, determined as eGFR < 30 ml/min
12. Elevated alanine aminotransferase (ALT) or aspartate aminotransferase (AST) > 5 times the upper limit of normal (ULN) or ALT or AST >3x ULN plus bilirubin >2x ULN
13. Bacterial sepsis, defined as documented bacteremia at the time of presentation or other active bacterial infection
14. Current participation in any research study involving investigational drugs or devices with the exception of dexamethasone, remdesivir, Baricitinib plus remdesivir as well as convalescent plasma and monoclonal antibodies, or any other therapy approved under emergency use in the region for treatment of COVID-19
15. Inability or unwillingness to give informed consent

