6.7 Premature Interruption or Withdrawal from Study Treatment

Prior to suspending the study treatment, permanently or temporarily, if possible, the investigator needs to contact the Medical Monitor to discuss the reason(s) for suspension.

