9 CONDUCT OF THE STUDY

9.1 Scheduling of Study Procedures

Patients hospitalized for COVID-19 with a prior history of CVD or at least one risk factor for CVD will be screened.

Day 0-1 -- Baseline assessments and Randomization and start of study medication

The following evaluations will be performed a baseline:

- Written informed consent
- Clinical assessment
- Demographics
- Medical History/Current conditions, including prior CV events and interventions
- Concurrent medication and CV medication history for the previous 24 weeks
- C-SSRS
- Vital signs, including heart rate (HR), blood pressure, height and weight
- Chest X-ray
- 12-lead ECG, including QTc interval assessment
- LVEF by echocardiography
- Assessment of Ordinal Outcome Scale
- Local laboratory assessments, including CBC, AST/ALT, alkaline phosphatase, bilirubin, creatinine/eGFR, INR, serum pregnancy test (in women with child-bearing potential only), glucose, total cholesterol, lymphocyte count and LDH
- Retention of frozen samples for hs-troponin, NT-proBNP, D-dimer, hs-CRP, ferritin, TNF-alpha, IL-1 beta, IL-6, IL-10 and additional parameters of interest
- Retention of frozen samples for CBD levels

Randomization and start of study medication (2.5 mg/kg b.i.d.) in the evening of Day 1 after all baseline assessments have been completed and all eligibility criteria are met. Randomization must be no later than 96 hours after hospital admission. Patients awaiting planned admission to hospital in an emergency room for less than 96 hours can be screened and enrolled into the trial.

Day 3

- Vital signs, including HR and blood pressure
- 12-lead ECG, including QTc interval assessment 5 hours post morning dose (time window 3.5 – 6 hours)
- Assessment of Ordinal Outcome Scale
- AE and SAE recording
- Recording of changes in concomitant medications
- Study drug dose increase to 5.0 mg/kg b.i.d., if previous dose is well-tolerated
- Study drug accountability
- Retention of frozen samples for hs-troponin, NT-proBNP, D-dimer, hs-CRP, ferritin, TNF-alpha, IL-1 beta, IL-6, IL-10 and additional parameters of interest

- Retention of frozen samples for CBD levels

Day 5

- Vital signs, including HR and blood pressure
- 12-lead ECG, including QTc interval assessment 5 hours post morning dose (time window 3.5 – 6 hours)
- Assessment of Ordinal Outcome Scale
- AE and SAE recording
- Recording of changes in concomitant medications

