If, following initiation of the investigational product, it is subsequently discovered that a study patient is pregnant or may have been pregnant at the time of investigational product exposure, including during at least 6 half-lives (18 days) after product administration, the investigational product will be permanently discontinued and the pregnancy will be reported to the Sponsor and the Contract Research Organization (CRO) within 24 hours of the site's awareness of the event. Worldwide Clinical Trials (WWCT) has been contracted as the CRO for this trial. Protocol-required procedures for study discontinuation and follow-up must be performed on the patient unless contraindicated by pregnancy. Other appropriate pregnancy follow-up procedures should be considered if indicated.

9.2.14.3 *Drug-Induced Liver Injury (DILI)*

Wherever possible, timely confirmation of initial liver-related laboratory abnormalities should occur prior to the reporting of a potential DILI event. All occurrences of potential DILIs, meeting the defined criteria below, must be reported as SAEs.

Potential DILI is defined as:

1. ALT or AST elevation $> 8 \times \text{ULN}$

OR
2. ALT or AST elevation $> 5 \times \text{ULN}$ for more than 2 weeks

OR

3. ALT or AST elevation $> 3 \times \text{ULN}$ and bilirubin $> 2 \times \text{ULN}$ or INR > 1.5 .

If a patient meets one of the above criteria, the study drug needs to be discontinued and the assessments of ALT, AST, bilirubin and alkaline phosphatase, as well as a physical examination need to be repeated every 24 hours until all abnormalities have normalized (in the investigator's opinion) or returned to the baseline state.

Elevations in ALT or AST $> 3 \times \text{ULN}$ or bilirubin $> 2 \times \text{ULN}$ alone, i.e., when not concomitant, are not grounds for withdrawal but are to be followed up, as above, within 72 hours of notice of abnormal results.

9.2.14.4 *Overdose*

All occurrences of overdose must be reported as SAEs. An overdose is defined as the accidental or intentional administration of any dose of a product that is considered both excessive and medically important.

9.2.14.5 *Drug-Drug Interactions*

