17.2 Schedule of Study Procedures

17.2.1 Clinical Assessments

	Study Days ⁶									
	0-1	3	5	7	14	21	28	45	60	
Consent	X									
Clinical assessment	X			X	X	X	X	X	X	
Demographics	X									
Medical History	X									
Vital Signs ¹	X	X	X	X	X	X	X	X	X	
Chest X-ray	X						X			
ECG	X	X	X	X	X	X	X			
Echocardiography	X						X			
Columbia-Suicide Severity Rating Scale	X						X			
Patient Impression of Change Questionnaire							X		X	
Ordinal Outcome Scale	X	X	X	X	X	X	X	X	X	
CMR (subset of patients at selected sites)							X	(X) ⁷		
Randomization ²	X									
Study medication ³	XX									
Study drug dose adjustment /accountability ⁴		X	X	X	X	X	X		X	
Concomitant Medication	X	X	X	X	X	X	X	X	X	
AE/SAE recording ⁵	X	X	X	X	X	X	X	X	X	

¹ Vital signs include heart rate and blood pressure; weight at baseline and at days 7, 14, 21, 28, 45 and 60; height at baseline

² Randomization on Day 1 after all baseline assessments, including local laboratory tests, have been completed, within 96 hours of hospital admission (or waiting for planned admission for <96 hours)

³ Start of study drug after randomization in the evening of Day 1, according to treatment schedule

⁴ At final visit accountability only

⁵ Adverse Event recording starts after informed consent is obtained

⁶ After hospital discharge, all scheduled assessments will be carried out as out-patient visits or home visits up to Day 7. After Day 7, all visits will be out-patient visits.

⁷ If CMR on Day 28 was not possible

PROPRIETARY AND CONFIDENTIAL

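### Exclusion 12 leaves out the INR half of the potential-DILI rule, so a patient can be randomized while already meeting a criterion for stopping study drug and reporting an SAE

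*Protocol*

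**What the plan says.** **Entry.** Exclusion 12 appears in Protocol 5.3 and in the synopsis and has two limbs. The first is ALT or AST above 5x ULN. The second is the combination "Alt or AST >3x ULN plus bilirubin >2x ULN" (5.3 wording; the synopsis is the same apart from capitalisation). No exclusion criterion mentions INR.

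**On treatment.** Protocol 9.2.14.3 defines potential DILI by three criteria: ALT or AST above 8x ULN; above 5x ULN for longer than two weeks; or above 3x ULN together with "bilirubin $> 2 \times \text{ULN}$ or INR > 1.5". The consequences are stated without qualification: "If a patient meets one of the above criteria, the study drug needs to be discontinued", and "All occurrences of potential DILIs, meeting the defined criteria below, must be reported as SAEs".

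**Timing of the INR.** INR is in the Day 0-1 panel in Protocol 9.1: "Local laboratory assessments, including CBC, AST/ALT, alkaline phosphatase, bilirubin, creatinine/eGFR, INR, serum pregnancy test". Footnote 2 of the schedule in 17.2.1 places randomization after those results: "Randomization on Day 1 after all baseline assessments, including local laboratory tests, have been completed". The site therefore holds the INR when it decides on eligibility.

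**The concern.** The bilirubin half of criterion 3 is mirrored in the entry rule and the INR half is not. A patient who falls in the difference can be given a first dose while already satisfying a liver criterion for which the protocol requires the drug to be stopped and an SAE filed. Section 9.2.14.3 has no express exemption for a value that was present at baseline.

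The protocol itself expects drugs that can produce each half of the combination. Appendix 17.10 lists warfarin, to be managed by INR monitoring, as a substrate of an enzyme that cannabidiol inhibits. It also lists remdesivir, which Protocol 6.8 permits, as raising transaminases. After baseline, the next scheduled ALT/AST and INR are on Day 7, by which time the schedule has taken the dose from 2.5 to 7.5 mg/kg twice daily.

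What is at stake is patient safety at entry and uniform handling across sites. Type I error, power and the comparison between arms are not affected.

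**Working it through.** No stated figure needs to be reproduced here; the check is one of logic.

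**1. Set each route to potential DILI against exclusion 12.** Criterion 3 contains two routes, so there are four in all.

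| Route (Protocol 9.2.14.3) | Blocked at entry by exclusion 12? |
|---|---|
| 1: ALT/AST >8x ULN | Yes, by the >5x limb |
| 2: ALT/AST >5x ULN for over two weeks | Yes, by the >5x limb |
| 3a: ALT/AST >3x ULN with bilirubin >2x ULN | Yes, by the bilirubin limb |
| 3b: ALT/AST >3x ULN with INR >1.5 | Only if ALT/AST >5x or bilirubin >2x ULN |

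Three of four are fully blocked. What remains open is ALT/AST >3x to 5x ULN, bilirubin ≤2x ULN and INR >1.5. An example is ALT 4x ULN, bilirubin 1x ULN, INR 2.0: eligible, and criterion 3 is met.

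**2. Allow for the missing bracket in criterion 3.** Its *and* and *or* can be grouped in two ways:

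- Reading A: ALT/AST >3x **and** (bilirubin >2x **or** INR >1.5).
- Reading B: (ALT/AST >3x **and** bilirubin >2x) **or** INR >1.5. Here a raised INR alone qualifies, whatever the ALT/AST.

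**3. Enumerate.** Take ALT/AST at 1, 3, 3.01, 4, 5, 5.01, 8 and 8.01x ULN; bilirubin at 1, 2, 2.01 and 3x ULN; INR at 1.0, 1.5, 1.51 and 2.5. That is 8 × 4 × 4 = 128 profiles. Each was tested with the ALT/AST elevation lasting either less or more than two weeks. Count the profiles that pass exclusion 12 and still meet a potential-DILI criterion:

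| | Exclusion 12 as written | With INR >1.5 added |
|---|---|---|
| Reading A | 12 | 0 |
| Reading B | 28 | 16 |

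The 12 under reading A are the open region in step 1: three ALT/AST values (3.01, 4, 5) × two bilirubin values (1, 2) × two INR values (1.51, 2.5). Reading B adds 2 × 4 × 2 = 16 profiles with ALT/AST ≤3x ULN and INR >1.5, giving 12 + 16 = 28. The revised exclusion removes the 12 and leaves the 16.

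Three results follow. The gap exists under either reading. Adding INR to exclusion 12 closes it completely under reading A. Under reading B a raised INR alone would still count, so criterion 3 needs its bracket as well. These counts test the logic only; they are not patient frequencies.

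**4. Compare with the protocol's other safety limits.** QTc above 500 msec is both an exclusion (5.3) and a stopping trigger (6.7.1). eGFR below 30 ml/min is both an exclusion (5.3) and a trigger for temporary suspension (6.7.2). For ALT/AST alone, entry (>5x) is stricter than stopping (>8x, or >5x for over two weeks). Among the potential-DILI routes, only the INR route has an entry rule looser than the stopping rule.

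**The case against.** The best counter-argument is that an unchanged baseline value is not an event, so the patient does not truly meet the stopping rule. Several texts support it:

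- Protocol 6.7.1 speaks of a liver abnormality developing, and says the investigator may suspend treatment.
- Protocol 9.2.14.1 defines an AE as something new or a worsening, and has pre-existing conditions recorded at enrolment.
- Protocol 9.2.14.3 asks, where possible, for abnormal liver results to be confirmed before reporting, and treats return to the baseline state as the end of follow-up.
- Under Protocol 6.7, before any suspension, "if possible, the investigator needs to contact the Medical Monitor to discuss the reason(s) for suspension".
- SAP 9.3.8 classes AEs with onset before first dose as pre-study.

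This stands in part: a site could reasonably decide not to act on an unchanged baseline value. But none of these texts is an exemption. Section 6.7.1 refers back to 9.2.14.3, where stopping is mandatory. The baseline-state wording only says when repeat testing may end. The SAP rule governs tabulation, whereas Protocol 9.2.14.6 requires SAE reporting from consent onward. Where the protocol wants a trigger limited to new findings it says so, as it does for eGFR in 6.7.2. Two sites could follow the text and act differently.

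A second argument is that INR above 1.5 on warfarin reflects anticoagulation rather than liver failure, so omitting it at entry is defensible, and a sentence exempting baseline values would be enough. The clinical point is fair. Such an exemption, however, would weaken the stopping rule for patients who enter with transaminases already above 3x ULN.

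A third is that reading B is strained, since criterion 3 opens with ALT/AST and the text after it says isolated ALT/AST or bilirubin elevations are not grounds for withdrawal. Reading A is indeed the likelier intent. That sentence does not mention INR, though, and the main gap does not depend on reading B.

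**Conclusion.** The concern holds and is minor. Exclusion 12 blocks three of the four potential-DILI routes at entry. A patient with ALT/AST >3x to 5x ULN, bilirubin ≤2x ULN and INR >1.5 passes it and meets criterion 3 under either grouping of its terms.

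The mismatch itself rests on no assumption beyond the protocol's wording. How often it would matter is unknown: the documents give no rate for the combination, and the warfarin and remdesivir entries show only that it is plausible, not that the two abnormalities occur together at baseline. No arm bias, loss of dose or effect on any efficacy analysis is claimed. Because the SAP Introduction reports that the study was terminated early, a correction now helps only further use of this text.

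**What to change.** Make two wording changes, in three places:

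1. In exclusion 12 (Protocol 5.3 and synopsis), make the second limb: *ALT or AST >3x ULN with either bilirubin >2x ULN or INR >1.5*. Do not add an anticoagulant exemption.
2. In Protocol 9.2.14.3, bracket criterion 3: *ALT or AST >3x ULN and (bilirubin >2x ULN or INR >1.5)*.

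Leave the on-treatment stopping rule otherwise as it is, so that a new ALT/AST rise above 3x ULN in an anticoagulated patient with a raised INR still stops study drug.

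With both changes, all four routes are blocked at entry and INR alone no longer qualifies. No new test and no SAP change are needed, because INR is already in the pre-randomization panel. The cost is a few more screen failures, mainly anticoagulated patients with raised transaminases.

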6 STUDY DESIGN

6.1 Summary of Study Design

Multi-center, double-blind, randomized, placebo-controlled, parallel group design. 1:1 randomization.

Screening (Assessment Day 0-1): Patients hospitalized for COVID-19 will be screened. If patient consent can be obtained, baseline assessments will be carried out: Physical examination (including vital signs), ECG (including QTc interval assessment), echocardiography, chest X-ray, local laboratory assessments, including CBC, AST/ALT, alkaline phosphatase, bilirubin, creatinine/eGFR, INR, serum pregnancy test (in women with child-bearing potential only), glucose, total cholesterol, lymphocyte count and LDH. Frozen samples will be retained for central analysis of CardiolRx™ levels, hs-troponin, NT-proBNP, D-dimer as well as inflammatory markers (hs-CRP, ferritin, TNF-alpha, IL-1 beta IL-6, IL-10). A C-SSRS will also be completed.

If all eligibility criteria are met, the patient will be randomized to either CardiolRx™ or placebo.

Study treatment will be initiated in the evening of Day 1, after all baseline assessments have been completed and the patient is randomized. Study medication must be taken with food. The maximum dosing period of patients will be 28 days.

Oral administration is as follows:

Study Day	a.m. dose [mg/kg of body weight] CardiolRx™ or placebo	p.m. dose [mg/kg of body weight] CardiolRx™ or placebo
1	N/A	2.5
2	2.5	2.5
3	2.5	5
4	5	5
5	5	7.5
6 - 28	7.5	7.5

If the next higher dose is not tolerated, the dose will be reduced to the previous tolerated dose. The highest tolerated dose will be administered until Day 28.

At each study visit, drug accountability will be done. New bottles of study medication will be dispensed at each study visit (Days 3, 5, 7, 14 and 21).

